8.3 Assessment of Efficacy

Primary efficacy (definitive cure at 12 months) of the two treatment regimens in subjects with PKDL will be measured clinically according to following criteria: complete resolution of papular and nodular lesions (flattening of 100% of lesions) and significant improvement (> 80% repigmentation) of macular lesions by 12 months after the end of treatment.

Secondary efficacy variables will be assessed by clearance of parasites by microscopy and qPCR before, during and after treatment during 12-month of follow up.

Secondary efficacy clinical assessment of PKDL lesions will also be done by the investigator at 12-months visit as per categories defined below:

- Category 1: All lesions have improved, and the majority of lesions have resolved. Any remaining lesions are only faintly visible as re-pigmentation is almost complete.
- Category 2: The majority of lesions show significant improvement some lesions have resolved.
- Category 3: No new lesions, but the majority of lesions show no or slight improvement.
- Category 4: New lesions have appeared and there is no or little improvement of other lesions

In addition, secondary efficacy variables will be assessed clinically (as per cure and categorical assessments described above) and by clearance of parasites by microscopy and qPCR at 24-months follow-up visit.

8.3.1 Clinical assessment and photo documentation of lesions

Clinical Assessment:

Clinical evolution will be recorded systematically by the Investigator using a scoring system (see below) and photographs at screening, Day 30, 3 months, 6 months and 12 months after

treatment onset. Definitive cure will be assessed at 12 months visit.

The same clinical assessment will be recorded at the 24 months follow-up visit.

PKDL Scoring:

To date, there was no standardized scoring method to objectively measure the extension of affected skin area in patients with PKDL. In order to improve PKDL evolution assessment, a scoring system was developed and validated by [name] and his team in Bangladesh. Using the diagram below, skin lesions will be plotted in squares corresponding to the affected skin areas of the body. The total number of squares containing lesions will be counted before (screening) and after treatment at Day 30, 3, 6, 12 and 24-months follow-up. The percentage of skin lesions cured by the treatment will be calculated as follows: total number of squares affected by the lesions at Visit 'X' ×100/total number of squares affected by the lesions at baseline. Indian sites will be trained and qualified to use this scoring system. Training records will be available in the Investigator file/TMF.

Protocol number: DNDi-MILT COMB-01-PKDL

Protocol Version/Date: V3.0, 25 Feb 2020

[figure not shown]
Figure 1: Scoring System

Patient's Initial:

Patient's ID:

Time: before / after treatment

Score (total number of squares affected by lesions):

Name of Physician:

Signature:

Date:

Photographs:

All lesions will be serially photographed under standardized conditions described in a photograph SOP (distance, light, camera, etc) at screening, Day 30 (EOT), 3-month, 6-month, 12-month, and at 24-month follow up visits.

Photographs taken during patient evaluation will be retained as source documents in the hospital files and in the Investigator's File. In addition, the electronic files with the photographs will be transferred to an independent external expert for remote blinded review of the photographs. The assessment of the investigator and the independent blinded reviewer will be compared. Cases of discrepancy will be assessed by a 3rd blind reviewer.

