10.6 Efficacy Analysis

Efficacy of the treatment will be assessed at 12 and at 24-month follow-up visit. The efficacy estimate will be reported as proportion of cured with its 95% confidence interval.

The data will be analysed as proportion, according to either mITT or PP populations.

Definitions

- **Cure**: Complete resolution of papular and nodular lesions (flattening of 100% of lesions) and significant improvement (> 80% re-pigmentation, as per scoring system, section 8.3.1) of macular lesions at 12 or at 24 months follow-up visits.
- Treatment Failure:

A patient will be considered a treatment failure:

- If rescue treatment is indicated by the investigator due to:
 - Non-response to treatment or worsening of PKDL lesions anytime during the treatment phase of the study
 - Occurrence of adverse events that leads to treatment discontinuation and require rescue treatment
 - Relapse: patient presented clinical response/improvement of lesions, but in subsequent follow-up visits the investigator observes appearance of new lesions and/or worsening of PKDL lesions, and indicates rescue treatment at any-time during follow-up period, including 24 months visit.

Or

• Patient did not fulfil the criteria for cure at the 12 or 24-months follow-up: presenting persistence of papular or nodular lesions and/or not significant improvement (< 80% re-pigmentation, as per section 8.3.1) of macular lesions.

• Lost to Follow Up: Patient did not turn up for 24 month follow up assessment and could not be contacted by health educators.

In addition, the overall clinical presentation of the patient will be assessed by the Investigator using the following categories ³⁴:

- Category 1: All lesions have improved and the majority of lesions have resolved. Any remaining lesions are only faintly visible as re-pigmentation is almost complete.
- Category 2: The majority of lesions show significant improvement, some lesions have resolved
- Category 3: No new lesions, but the majority of lesions show no or slight improvement.
- Category 4: New lesions have appeared and there is no or little improvement of other lesions

The proportion of PKDL patients in category 1, 2, 3 and 4 with its 95% confidence interval will be summarized per study arm, at 12 and at 24 months follow-up visits.

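### Section 10.6 takes macular re-pigmentation from a score that counts affected squares, so the primary endpoint measures extent under the name of pigment; the printed percentage is also inverted

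*Protocol*

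**What the plan says.** The synopsis and sections 2.2.1 and 8.3 define cure at 12 months as complete flattening of papules and nodules plus more than 80% re-pigmentation of macules. Section 2.2.2 repeats this for 24 months. None of these places names an instrument for the pigment part.

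Section 10.6 names one. Cure requires "significant improvement (> 80% re-pigmentation, as per scoring system, section 8.3.1) of macular lesions at 12 or at 24 months follow-up visits", and one route to failure is "not significant improvement (< 80% re-pigmentation, as per section 8.3.1) of macular lesions".

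Section 8.3.1 describes that instrument. It fills the lack of a standard method "to objectively measure the extension of affected skin area in patients with PKDL". Lesions are plotted on a body diagram: "The total number of squares containing lesions will be counted before (screening) and after treatment". The derived percentage is introduced with "The percentage of skin lesions cured by the treatment will be calculated as follows" and then given as "total number of squares affected by the lesions at Visit 'X' ×100/total number of squares affected by the lesions at baseline". The scoring form has one result field, the number of affected squares.

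Section 10.6 also has the investigator place each patient in one of four overall categories. Category 1 requires that all lesions have improved and most have resolved, and it accepts that any "remaining lesions are only faintly visible as re-pigmentation is almost complete".

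**The concern.** The criterion is worded as recovery of pigment, but the instrument assigned to it records only whether a square contains a lesion. The text of 8.3.1 has no pigment grade and no rule for when a fading macule stops counting. A statistical analysis plan cannot settle this by analysis, because a pigment level cannot be recovered from a count of squares.

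At stake is what the primary endpoint can claim. A cure rate reported as re-pigmentation would in fact be a rate of clearance of affected area, and the two can disagree for the same patient. Section 1.4 makes partly re-pigmented macules at 12 months plausible. It notes the difficulty of judging cure in macular lesions. It also describes a large Bangladeshi field series in which patients without significant re-pigmentation at 12 months improved at later visits.

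**Working it through.** The plan states no figure for agreement between the score and re-pigmentation, so there is none to reproduce. The check applies the 8.3.1 score to worked patients.

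**Inputs.** B = affected squares at baseline; V = affected squares at the visit; cut-off more than 80% (section 10.6). B = 40 and the pigment levels below are assumptions for illustration.

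**Step 1: the formula as printed, 100 x V/B.**
- Full clearance, V = 0: 100 x 0/40 = 0%.
- No change, V = 40: 100 x 40/40 = 100%.

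This is the percentage of squares remaining. Against a cut-off of more than 80%, a cleared patient would miss it and an unchanged patient would pass. The label shows that the complement was meant: 100 x (B - V)/B.

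**Step 2: the complement against the cut-off.**
- V = 7: 100 x 33/40 = 82.5%, cured.
- V = 8: 100 x 32/40 = 80.0%, not more than 80%, so not cured.

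Lesions left in 20% or more of the baseline squares therefore rule out cure. The pigment level in those squares does not enter the formula. Exactly 80% also meets neither the cure wording (above 80%) nor the failure wording (below 80%).

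**Step 3: a patient for whom score and pigment disagree.** Assume 28 squares clear and 12 with faint macules at 95% re-pigmentation.
- Average re-pigmentation over baseline squares: (28 x 100 + 12 x 95)/40 = 3940/40 = 98.5%.
- Squares cleared: 100 x 28/40 = 70%, not cured.
- Category: if lesions are spread about evenly over the squares, most have resolved and the rest are faint with almost complete re-pigmentation. This fits Category 1.

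The same patient is a failure on the primary endpoint and can be in the best category of the secondary one.

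**Step 4: what cannot be computed.** The protocol gives no distribution of residual pigment, so the share of such patients cannot be derived. As an assumed range only, suppose 5%, 10% or 20% of patients cured by pigment were classed as failures, starting from the anticipated 85% cure rate in section 10.1:
- 0.85 x 0.95 = 80.8%
- 0.85 x 0.90 = 76.5%
- 0.85 x 0.80 = 68.0%

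**The case against.** The strongest defence is that 10.6 makes the score the operational definition. Re-pigmentation as per the scoring system can be read as more than 80% of the baseline affected area no longer showing lesions. On that reading the trial is internally consistent. This has force, and it is why renaming the criterion is enough. But the endpoint sections still promise re-pigmentation, and nothing tells a reader that cleared area is meant.

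Section 8.3.1 also calls the score validated, provides training for the Indian sites, and adds blinded photograph review with a third reader for disagreements. These steps support consistent use. The section does not say that the score was validated for pigment, and it gives the photograph readers no pigment threshold. Assessors may choose to leave faint macules unmarked, but the text does not tell them to. The scoring diagram is not reproduced in the available text, so any marking instruction on it cannot be judged.

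Three stronger readings are tempting and are not supported:
- A reader might infer that a patient with faint macules in all 40 squares is a Category 1 failure. Category 1 requires most lesions to have resolved, so that patient is not Category 1. A mixed case such as Step 3 is needed.
- A reader might infer that 33 squares clear and 7 unchanged is a false cure. Averaged over the affected area, that patient is 82.5% recovered by either measure, so there is no contradiction unless the 80% is applied to each lesion separately.
- A reader might infer from the figure of over 90% macular disease in section 1.2 that most of the trial is affected. That figure is for Bangladesh, one of three sites. By the monthly numbers in section 4 (4-5, 10-15 and 4-5 patients), that site contributes between 4/(4+5+15) = 17% and 5/(5+4+10) = 26% of patients. Section 1.2 says Indian patients often have macules within a mixed rash, but gives no proportion.

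**Conclusion.** The mismatch is real and lies in the primary endpoint: 10.6 assigns a pigment criterion to an instrument that measures extent, and 8.3.1 labels the percentage remaining as the percentage cured. On the evident intended reading, visible lesions in 20% or more of the baseline squares prevent cure whatever their pigment, so a patient who fits Category 1 can be counted as a failure.

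This rests on two assumptions: that the complement of the printed ratio is intended, and that a faintly visible macule counts as a lesion, as the plain wording suggests. The documents support the statement that such misclassification can occur. They do not support a frequency, and the reduced cure rates in Step 4 are not a forecast. Nor do they support the inference that cure rates would be computed with the inverted formula; its label makes the intention clear, but the text needs correcting.

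**What to change.** 1. In the synopsis and sections 2.2.1, 2.2.2, 8.3 and 10.6, state the macular criterion as what the score measures: a reduction of more than 80% from baseline in the number of affected squares. In the same edit, word the failure definition as 80% or less, so that exactly 80% is covered.
2. In 8.3.1, correct the formula to 100 x (baseline squares - visit squares)/baseline squares.
3. If the sponsor wants a true re-pigmentation criterion instead, 10.6 should stop citing the square count as its measure.
4. In either case, cross-tabulate cure with Categories 1-4 at 12 and 24 months. Both are already collected, and the table would show how many patients are classed differently.

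Items 1, 2 and 4 need no new data and leave the validated count unchanged. The downside is that the endpoint is then described as extent, so it is less directly comparable with earlier cure rates based on re-pigmentation, such as the 86.5% field series in section 1.4.

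A rule that a square stops counting once its macule is more than 80% re-pigmented is less attractive. It stacks two 80% thresholds: 33 squares at 81% and 7 at 0% average 33 x 81/40 = 66.8%, yet the patient would be cured. It would also alter the instrument when 12-month scores may already exist, since protocol V3.0 provides for patients past that visit.

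### The section 8.3.1 formula labelled as percentage cured gives the percentage still affected, and section 10.6 refers the 80% macular threshold to it

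*Protocol*

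**What the plan says.** Section 8.3.1 describes a body diagram divided into squares. "The total number of squares containing lesions will be counted before (screening) and after treatment", with post-treatment counts at Day 30 and at 3, 6, 12 and 24 months. The calculation is then given: "The percentage of skin lesions cured by the treatment will be calculated as follows: total number of squares affected by the lesions at Visit" X, multiplied by "100/total number of squares affected by the lesions at baseline". The scoring form shown in the text has one field for the result, "Score (total number of squares affected by lesions").

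Section 10.6 links the outcome definitions to this section. Cure needs complete flattening of papules and nodules together with "significant improvement (> 80% re-pigmentation, as per scoring system, section 8.3.1) of macular lesions at 12 or at 24 months follow-up visits". A patient who does not meet the cure criteria fails through persistent papules or nodules and/or "not significant improvement (< 80% re-pigmentation, as per section 8.3.1) of macular lesions".

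Section 8.3 states the primary criterion, timed from the completion of therapy, without a calculation: "complete resolution of papular and nodular lesions (flattening of 100% of lesions) and significant improvement (> 80% repigmentation) of macular lesions by 12 months". Section 2.2.1 does the same.

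**The concern.** The formula is named for what has been cured, but its numerator counts what is still affected. Section 8.3.1 contains no other formula, and section 10.6 points there for the 80% threshold. The only stated calculation for the macular component of the primary endpoint therefore contradicts the endpoint. If one user programs it as written and another quietly applies the complement, the same patient gets opposite results on that component. The 24-month efficacy endpoint uses the same rule.

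A second and less certain matter is what is counted. The 80% rule concerns macular lesions, and papules and nodules have their own rule (complete flattening). The text nevertheless counts squares containing lesions of any kind and records one total. In a patient with mixed lesions, squares that held only papules or nodules could raise the figure used to judge macular response.

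**Working it through.** **Inputs.** Formula and counting rule from section 8.3.1; thresholds from section 10.6. The protocol gives no square counts, so every count below is an illustrative assumption. B is squares affected at baseline and X is squares affected at the visit.

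**Step 1. The formula as written.** Written value = 100 × X / B. Value implied by its label = 100 × (1 − X / B). With B = 20:

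| X at visit | As written | Above 80%? | Complement | Above 80%? |
|---|---|---|---|---|
| 0 (full clearance) | 0% | no | 100% | yes |
| 3 | 15% | no | 85% | yes |
| 4 | 20% | no | 80% | no |
| 17 | 85% | yes | 15% | no |
| 20 (no change) | 100% | yes | 0% | no |
| 24 (spread) | 120% | yes | −20% | no |

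As written, full clearance misses the macular component, and persistence or spread meets it. The two columns add to 100% in every row, so the formula returns the complement of the quantity it names.

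The row X = 4 also shows a gap at the boundary. Exactly 80% is neither above 80% (cure) nor below 80% (failure).

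**Step 2. Pooling, with the direction corrected.** Let P be baseline squares with only papular or nodular lesions, all counted as unaffected once flat. Let M be baseline macular squares, of which m remain.

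- Pooled clearance = 100 × (1 − m / (P + M))
- Macular clearance = 100 × (1 − m / M)

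| P | M | m | Pooled | Macular |
|---|---|---|---|---|
| 16 | 4 | 3 | 1 − 3/20 = 85% | 1 − 3/4 = 25% |
| 25 | 25 | 9 | 1 − 9/50 = 82% | 1 − 9/25 = 64% |
| 0 | 50 | 9 | 1 − 9/50 = 82% | 1 − 9/50 = 82% |

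The pooled figure exceeds 80% whenever m is below 0.2 × (P + M). If macular squares make up less than 20% of the baseline total, all of them can persist (m = M) and the pooled figure still passes. With macular lesions only (P = 0), the two figures are equal and pooling has no effect.

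**The case against.** A reader might infer from the formula that the primary endpoint itself is inverted. The documents do not support that. Sections 2.2.1, 8.3 and 10.6 all ask for more than 80% re-pigmentation, which is the right direction; one supporting formula conflicts with them. A score of 0% for a cleared patient would probably be noticed. Section 8.3.1 also sends the photographs to an independent blinded reviewer, with a third blind reviewer for discrepancies. The protocol does not say how that review enters the endpoint, but it makes unnoticed misclassification less likely. These points lower the chance of harm. They do not make the formula correct, and section 10.6 still cites it.

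A reader might also call the patient with 17 of 20 squares left a literal cure. That goes too far. Cure has two parts, and 85% under the formula as written meets only the macular part.

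On pooling, the other side is stronger:

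- Section 10.6 speaks of macular lesions, so applying the score to macular squares only is a natural reading.
- Figure 1 is not visible, and a lesion-type code on the diagram cannot be excluded.
- The example needs nodular-only squares kept apart from macular ones, and needs a flattened nodule to leave an unaffected square. Where lesion types share a square, a persisting macule keeps it counted and the overstatement shrinks.
- Section 1.2 calls the Indian rash often polymorphic, which is less than usual, and warns that most reported cases come from tertiary referral centres. In Bangladesh it reports a macular rash in more than 90% of patients, and pooling is harmless where the rash is macular only.

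What remains is that the visible text counts all lesion squares, records one total and does not state the restriction.

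**Conclusion.** The formula in section 8.3.1 is wrong as written. It yields the percentage still affected under the name of percentage cured, and section 10.6 draws the macular thresholds for cure and failure from it. Taken literally, it reverses the macular component: with 20 baseline squares, 0 left gives 0% and 17 left gives 85%. This holds with high confidence and does not depend on the assumed count, because the written and intended values always sum to 100%. It does not show that any patient has been misclassified.

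The pooling point holds with medium confidence. It rests on the visible text alone, on lesion types occupying separate squares, and on flattened papules or nodules counting as cleared. Under those assumptions the pooled figure can overstate macular response substantially (85% against 25% in the example). It is an ambiguity to close, not a demonstrated error.

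**What to change.** 1. In section 8.3.1, replace the formula with: percentage cured = 100 × (1 − squares affected at Visit X / squares affected at baseline). This is a one-line change and needs no new data, because the counts are already recorded.

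2. In section 10.6, state that the 80% rule is applied to squares with macular lesions at baseline. A patient with none has a zero denominator, so say that this patient is judged on the flattening criterion alone. In the same edit, assign exactly 80% to cure or to failure.

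3. If lesion type was not marked on the diagrams, do any recoding from the stored photographs, blind to treatment arm. The trial is open label, and a footnote to the schedule of events (section 5) allows for patients who had already completed 24 months before version 3.0, so some recoding would be retrospective.

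The cost of items 2 and 3 is the recoding work and a departure from a scoring form that section 8.3.1 describes as validated. That departure should be recorded as a limitation. If Figure 1 already separates lesion types, item 2 is only a wording change and item 3 falls away.

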3.1 Study design

This is a non-comparative, open label, randomized phase II clinical trial to assess the safety and efficacy of Ambisome[®] monotherapy (5 x 4 mg/kg IV given twice per week at a total dose of 20 mg/kg given) and a combination of Ambisome[®] (5 x 4 mg/kg IV given twice per week at a total dose of 20 mg/kg) plus miltefosine orally daily (allometric dosing BID) for three weeks for PKDL patients in India and Bangladesh.

In order to have representatives of PKDL patients from different countries and to increase recruitment capacity, three sites will participate in this study; 2 sites in India – KMRC, Muzzafarpur and RMRI, Patna and one site in Bangladesh – icddr,b (Surya Kant Kala Azar Research Centre as satellite site of icddr,b).

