7.6 Blinding and procedures for unblinding

Not applicable. This is an open label study.

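### The blinded photograph review has no stated role in primary cure, which section 10.6 ties to a score recorded by the open-label investigator

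*Protocol*

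**What the plan says.** Treatment is not blinded. Section 7.6 reads "Not applicable. This is an open label study", and section 3.1 describes the design: "This is a non-comparative, open label, randomized phase II clinical trial to assess the safety".

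Section 8.3 introduces the primary endpoint without naming who judges it: "Primary efficacy (definitive cure at 12 months) of the two treatment regimens in subjects with PKDL will be measured clinically according to following criteria". The criteria are full flattening of papular and nodular lesions and more than 80% re-pigmentation of macular lesions.

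Section 8.3.1 names the person who scores: "Clinical evolution will be recorded systematically by the Investigator using a scoring system". The score is the number of squares on a body diagram that contain lesions, entered on a form with the physician's name and signature. The same paragraph places the judgement of definitive cure at the 12-month visit.

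Section 10.6 then defines cure by that instrument: "significant improvement (> 80% re-pigmentation, as per scoring system, section 8.3.1) of macular lesions at 12 or at 24 months follow-up visits". A patient is also a failure "If rescue treatment is indicated by the investigator due to" one of several listed reasons.

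Separately, section 8.3.1 sends the photographs to an independent external expert for blinded reading. On what follows, it says: "The assessment of the investigator and the independent blinded reviewer will be compared. Cases of discrepancy will be assessed by a 3rd blind reviewer".

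**The concern.** The protocol provides two kinds of reading of the same lesions, one unblinded and one blinded, and does not say which of them is the analysed outcome. The only reading with a written path into the cure definition is the unblinded one.

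This matters because part of the endpoint is a judgement. Someone must decide whether a macule has re-pigmented enough for its square to stop counting as affected. Section 1.4 cites an antimonial series in which assessing cure was found difficult, above all for macular lesions. Section 1.2 says that more than 90% of patients in Bangladesh have a macular rash.

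The primary efficacy result is a cure proportion per arm with a 95% confidence interval. The trial is non-comparative, so the main risk is a cure rate that is too high in each arm taken alone. An interval for a proportion reflects sampling variation only and says nothing about an assessor who leans towards cure.

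There is also a reproducibility problem. Two analysts could both follow this text and report different primary results, one from the investigator's score and one from the reading after the third review. If the choice is settled once investigator results are visible, it can follow the data.

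**Working it through.** **Step 1. The planned precision (section 10.1).** Inputs: anticipated cure 85%, precision 10 points, 95% confidence, 50 evaluable and 63 randomised per arm.

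- n = 1.96² × 0.85 × 0.15 / 0.10² = 48.98, rounded up to 49. The stated minimum of 50 is consistent with this.
- Half-width at n = 50: 1.96 × √(0.85 × 0.15 / 50) = 9.9 points.
- Half-width at n = 63: 1.96 × √(0.85 × 0.15 / 63) = 8.8 points.

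These figures assume that each patient's cure status is recorded without error.

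**Step 2. Which reading reaches the primary outcome.**

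| Section | What it says about the assessor |
|---|---|
| 8.3 | None named for primary cure; the investigator is named for the four-category assessment |
| 8.3.1, clinical assessment | The investigator records the score |
| 8.3.1, photographs | Blinded expert, comparison, third blinded reviewer; no consequence for the outcome stated |
| 10.2 and 10.3 | Cure proportion, populations and missing data; no mention of blinded readers |
| 10.6 | Cure by the 8.3.1 score; rescue failure by the investigator; no mention of blinded readers |

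The chain from 10.6 to the score, and from the score to the investigator, is complete. No sentence links the blinded or third reading to cure. Section 8.3.1 also does not say which visits the review covers, or whether the remote reader counts squares.

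**Step 3. How few patients matter.** If k patients are scored cured who would not be cured on a blinded reading, the rate rises by k/n.

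- k = 3, n = 63: 4.8 points.
- k = 6, n = 63: 9.5 points.
- k = 7, n = 63: 11.1 points.
- k = 3, n = 50 (evaluable patients only): 6.0 points.

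At 85% true cure, 63 × 0.15 = 9.45 patients per arm are not cured, so 3 patients are about one third of them (3/9.45 = 32%).

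**Step 4. The same as a rate.** Let f be the share of re-scorable non-cures called cured, and r the share of non-cures that no reading can change (rescue, or missing counted as failure). The shift is (1 − 0.85) × (1 − r) × f. Both f and r are assumptions, since the documents give neither.

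| f | r = 0 | r = 0.5 |
|---|---|---|
| 1/5 | 3.0 points | 1.5 points |
| 1/3 | 5.0 points | 2.5 points |
| 1/2 | 7.5 points | 3.75 points |

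The column r = 0 is an upper bound for each f. Misreading in the other direction, with cured patients scored as not cured, would reduce the shift.

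**The case against.** The strongest reply is that a third blinded reading, called for only when the first two disagree, is most naturally adjudication. Section 8.3 names no assessor for primary cure, whereas the four-category assessment is expressly the investigator's. Section 10.6 refers to section 8.3.1, which contains the blinded review as well as the score. On this view the protocol is merely silent on a derivation rule that the SAP may supply.

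Part of this stands. A reader might infer that the blinded review decides nothing; the text does not support that, because the third reviewer suggests that the sponsor intended adjudication. No sentence says that the investigator's reading prevails either. But 8.3.1 says only that discrepant cases are assessed again. It does not call the result final, and 10.6 points to the scoring system, which 8.3.1 gives to the investigator. Whose reading counts is part of the endpoint definition, and the protocol has chosen to set out both the readers and the cure definition. They should connect.

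Other points for the defence also stand. The square count is described as validated, Indian sites are to be trained and qualified in it, and photographs follow an SOP, all of which limits subjectivity. Parasitological results do not depend on the lesion score, so cure is not the only efficacy output.

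Two further inferences should be resisted. A reader might expect bias in favour of the combination arm, but no between-arm efficacy comparison is described, so this matters only if the arms are compared informally. A reader might also take the background's 86.5% under routine field assessment and 80% in a trial with independently evaluated photographs, both at 30 mg/kg, as a measure of assessor bias. Criteria and populations may differ, so it is not.

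**Conclusion.** The point holds as a gap between sections 8.3.1 and 10.6. A blinded review with third-reader resolution is planned but has no stated role in primary cure, and the literal path leads to the open-label score. It should be corrected, because it leaves the primary outcome open to two readings and exposes it to assessor error that the confidence interval does not cover.

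The size is unknown. The illustration that 3 re-scored patients of 63 shift the rate by about 5 points shows sensitivity, not expected bias. A reader might take the 3 to 7.5 points at r = 0 as a forecast. That is not supported: those values rest on assumed error rates in one direction, and they treat every non-cure as re-scorable although rescue and missing-outcome failures are not. The planned sample size is unaffected.

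**What to change.** State in sections 8.3.1 and 10.6 that, for the primary analysis at 12 months and the secondary analysis at 24 months:

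- cure status is the investigator's reading where the blinded reviewer agrees;
- where they differ, the third blinded reviewer's reading is final;
- the blinded readers apply the same cure criteria as the investigator.

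For a yes/no outcome this amounts to the majority of up to three readings, two of them blinded, so the unblinded reading cannot settle cure alone. Report the investigator-only result as a sensitivity analysis, with agreement between readers. Failure through rescue stays as already defined and remains an unblinded route to failure.

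The cost is small: no new patients, visits or reader roles. It is mainly wording, but the instructions to the blinded readers may need to be extended, because 8.3.1 does not say that they apply the square count. The downside is that flattening of papules and nodules is harder to judge on photographs. The investigator-only sensitivity analysis addresses this by showing how far the result depends on it.
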